5. DEFINITIONS

5.1. Baseline Definition

For efficacy, safety (except ALT, AST, lipids, and vital signs), and biomarkers each subject's baseline value for that measurement will be defined as the last non-missing value collected on or before the day of first study drug dose, or randomization date + 5 days if subjects have never been dosed. Other baseline values, such as demographics and pertinent medical history etc., is defined as last available value before randomization date.

The definition of baseline of lipid panel labs is the average of last non-missing screening fasting values and Study Day 1 value (Pre-dose, fasting).

The definition of baseline vital signs is the average of the last non-missing screening values and Study Day 1 value (Pre-dose). If there is Case Report Form (CRF) average value on duplicate measurements of BP and/or Pulse on Study Day 1, only the individual values will be included in the baseline derivation.

Baseline ALT and AST were defined as below:

Table 3: Baseline Definition for ALT and AST Values

ALT/AST Screening Assessments			Day 1 ALT/AST Assessment	Baseline Value
Assessment 1	Assessment 2	Assessment 3 (if applicable)		
Normal	Normal	Not applicable	Any	Average of Assessment 1, Assessment 2 and Day 1 (3 tests)
Normal	Abnormal and ≤40% increase from Assessment 1	Not applicable	Any	Average of Assessment 1, Assessment 2 and Day 1 (3 tests)
Normal	Abnormal and >40% increase from Assessment 1	Normal or ≤40% increase from Assessment 1	Any	Average of Assessment 1, Assessment 2, Assessment 3 and Day 1 (4 tests)
		Abnormal and >40% increase from Assessment 1	Not applicable, subject excluded	Not applicable, subject excluded
Abnormal	≤40% increase from Assessment 1	Not applicable	Any	Average of Assessment 1, Assessment 2 and Day 1 (3 tests)
Abnormal	>40% increase from Assessment 1	≤40% increase from Assessment 1	Any	Average of Assessment 1, Assessment 2, Assessment 3 and Day 1 (4 tests)
		>40% increase from Assessment 1	Not applicable, subject excluded	Not applicable, subject excluded

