MRI-PDFF	X			X	X				X	X			At Screening, MRI-PDFF should ideally be done before liver biopsy. At Screening, a historical MRI-PDFF assessment performed within the last 3 months prior to screening may be acceptable if the images are available and evaluable by the central imaging vendor. On treatment, MRI-PDFF should ideally be done within ± 7 days of the target visit date. If out of the window, MRI-PDFF should be performed as close to the target visit date.
cT1	X			X	X				X	X			Iron-corrected T1 mapping. Applicable only at sites capable of conducting cT1 imaging. At Screening, a historical cT1 assessment performed within the last 3 months prior to screening may be acceptable if the images are available and evaluable by the central imaging vendor.
Liver/Spleen volume and pancreatic fat	X			X	X				X	X			To be done at the same time as MRI-PDFF. At Screening, a historical liver/spleen volume and pancreatic fat assessment performed within the last 3 months prior to

Assessments	Screening Period ¹	Treatment Period										FU Period		Notes:	
		Main Study					Extension Study								
Study Day		1 ²													
Study Weeks	-12 to 0		4 ³	8 ⁴	12 ³	16 ⁴	24 ³	26 ⁵	30 ⁴	38 ³	48 ³	ET ^{3,6}	51 ^{7/} EOS		
Visit window (days)			±2	±7	±7	±7	+7	+7	±7	±14	+14		±14		
														screening may be acceptable if the images are available and evaluable by the central imaging vendor.	
Bone Mineral Density (BMD) by Dual X Ray Absorptiometry (DXA) ^r		X				X				X	X			r. DXA should be done within -14/+7 days of the target visit date. If out of the window, DXA should be performed as close to the target day as possible.	
Plasma for bone biomarkers analysis		B		X		X				X	X			Includes CTX, P1NP, and osteocalcin; refer to Appendix 2 (Section 10.2).	
Endogenous FGF21 ^s		B												s. Baseline samples of endogenous FGF21 will be obtained in all subjects; additional samples will be obtained at the immunogenicity follow-up visits (See Table 2). Endogenous FGF21 samples (baseline and follow-up visit) will be analyzed only in subjects with neutralizing ADAs.	
Immunogenicity		B	X	X	X		X		X	X ^t	X			t. See Table 2 for immunogenicity follow-up.	
Pharmacogenomic (DNA) blood sampling		X												Optional.	
Blood sample for exploratory biomarkers		X				X			X	X					
Adverse event monitoring ^u	X	X	<=====X=====>						X	X				u. The sites may take non-personally identifying photographs of potential injection site reactions (optional).	
Concomitant medications	X	X	<=====X=====>						X	X					

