6.1. Investigational Product Administered

IP will be administered SC to the abdomen region by qualified personnel in the clinic or in the subject's home, or by the subject/subject's caregiver following required training on IP administration. Some IP administrations will occur at the subject's home.

ARM	Active– liquid formulation	Placebo (control)
Investigational product	pegozafermin	Matching placebo
Type	Biologic	Chemical solution
Dose Formulation	Each 1.1 mL vial contains [REDACTED] mg of pegozafermin in Tris buffer solution (containing [REDACTED] [REDACTED] at a concentration of [REDACTED] mg/mL	Each 1.1 mL vial contains Tris buffer solution (containing [REDACTED] [REDACTED]
Unit Dose Strength(s)	mg	Not applicable
Dosage Level(s)^a	QW 15 mg 30 mg	QW Matching placebo will be injected QW.
	Q2W 44 mg	Q2W Matching placebo will be injected Q2W.
Route of Administration	SC injection	SC injection
Administration Instructions	SC injection of the IP will be performed by qualified site staff when the subject attends Day 1 visit. Subjects and/or caregivers may also be trained on self-administration and thereafter self-administer the IP with staff witnessing on Day 1. Further doses will be administered at home by subject, subject's caregiver, or home healthcare services. Details on administration at home, including training requirements, are provided in the Home Administration Instructions or Pharmacy Manual.	
Sourcing	Provided centrally by the Sponsor	Provided centrally by the Sponsor
Packaging and Labeling	IP (pegozafermin and placebo) is supplied as a sterile, preservative-free, liquid formulation in a single-use Type 1 clear glass vial for SC injection. Each vial will be labeled per country requirement.	

^a The actual doses will be $\pm 5\%$ the mg dose due to technical considerations related to drug withdrawal from the vials into the syringes for injection. This difference is considered negligible for subject exposure.

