4.1.5. Safety Endpoints

- Frequency and severity of TEAEs and SAEs
- Number of subjects who discontinued due to TEAEs and due to related TEAEs
- Incidence and shifts of clinically significant physical examination findings, ECG data and laboratory abnormalities; safety laboratory evaluations include hematology, blood biochemistry and urinalysis, serum, salivary, and urinary cortisol as appropriate
- Change from baseline in
 - Insulin-like growth factor 1 (IGF-1)
 - Bone biomarkers: Carboxy-terminal collagen crosslinks (CTX), N-terminal propeptide of type 1 collagen (P1NP) and osteocalcin
 - Thyroid stimulating hormone (TSH)
- Absolute and % change from baseline in lumbar spine, total hip, and femoral neck bone mineral density (BMD) as assessed by dual X-ray absorptiometry (DXA)
- Incidence and characteristics of anti-drug antibodies (ADA) and neutralizing antibody (NAb) after dosing (e.g., titer and binding specificity, to the FGF21 and polyethylene glycol [PEG] part of pegozafermin)
- Impact of the presence of ADAs on serum pegozafermin concentrations and clinical safety

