5.3. Study Day

The day a subject receives their first dose of IP will be considered as Study Day 1.

If a subject is randomized but never dosed, study day will be calculated using the randomization date and randomization date will be set to Study Day 1.

If date of interest occurring on or after the relative date, relative day is calculated as: date of interest – relative date + 1, else if date of interest occurring prior the relative date, relative day is calculated as: date of interest – relative date. Data will be presented on listings in order of site number/subject number, assessment date and assessment (in order collected on CRF, unless specified otherwise). Dates will be presented in the format of YYYY-MM-DD.

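### The DXA window lets the first scan fall up to 7 days after first dose, but the SAP baseline rule rejects such a scan, so change in BMD cannot be computed for that subject

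*SAP*

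**What the plan says.** **Schedule.** In Protocol 1.3 (Table 1), copied in SAP Appendix 1, the Screening cell of the DXA row is empty. The first scan is at Day 1; later ones are at Week 24, Week 48 and early termination. Note r is attached to the row label and reads "DXA should be done within -14/+7 days of the target visit date". For scans that miss the window it adds "If out of the window, DXA should be performed as close to the target day as possible". Neither sentence singles out a visit or requires the first scan to precede dosing. The Day 1 mark is a plain X, not the B that the table uses for predose assessments.

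**Day 1 is the dosing day.** Protocol 6.1 says "SC injection of the IP will be performed by qualified site staff when the subject attends Day 1 visit", and SAP 5.3 says "The day a subject receives their first dose of IP will be considered as Study Day 1".

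**Baseline.** For efficacy, safety and biomarker measures, SAP 5.1 takes "the last non-missing value collected on or before the day of first study drug dose". ALT, AST, lipids and vital signs have rules of their own. An allowance of 5 days after randomization exists, but only for subjects who were never dosed.

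**Endpoint and analysis.** Absolute and percent change in BMD at the lumbar spine, total hip and femoral neck is a named safety endpoint in the Main Study (SAP 4.1.5) and the Extension (SAP 4.2.3). SAP 7.10.5 plans descriptive summaries of value, change and percent change by treatment group. It gives no separate baseline rule for BMD.

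**The concern.** Two operative rules meet at the Day 1 DXA and do not agree. The schedule tells the site that a scan up to a week after the visit is in window. The SAP tells the programmer that a value dated after the first-dose day cannot be a baseline. With no Screening scan to fall back on, a subject for whom both rules are followed has a near-baseline scan on file but no baseline BMD.

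At stake is bone safety information. Change from baseline is what the endpoint asks for in both parts of the study, and a baseline that was not captured cannot be obtained later. The planned 15 mg QW arm is small enough that one or two such subjects would be noticeable.

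**Working it through.** The plan states no figure for this point, so the check is date arithmetic and a comparison of texts.

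**1. Dates that the window allows around Day 1.** The SAP 5.3 study-day formula is date minus Day 1 date, plus 1 on or after Day 1, with nothing added before it.

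- Earliest: 14 days before gives Study Day -14.
- Latest: 7 days after gives 7 + 1 = Study Day 8.
- Dates allowed: 14 before + Day 1 + 7 after = 22.

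**2. The same dates against SAP 5.1.**

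| Study Day of first scan | Dates | In window (note r) | Baseline (SAP 5.1) |
|---|---|---|---|
| -14 to -1 | 14 | yes | yes |
| 1 | 1 | yes | yes |
| 2 to 8 | 7 | yes | no |

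So 14 + 1 = 15 dates satisfy both rules, and 7 satisfy the schedule only. The out-of-window sentence also permits scans later than Day 8, which fail in the same way.

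**3. Whether another rule rescues Days 2 to 8.**

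- The exceptions in SAP 5.1 do not include BMD.
- The 5-day allowance covers never-dosed subjects only, and they are outside the Safety Analysis Set.
- SAP 7.10.5 and Protocol 8.2.4 add no timing rule.
- Protocol Section 8 lets a routine procedure done before consent serve as baseline if it falls within the schedule's timeframe. This may help an occasional subject but is not a general remedy.

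**4. What the subject loses.** Change and percent change need a baseline, so they are missing at Week 24 and Week 48 for all three sites. Absolute values at those visits are still available and are summarized under SAP 7.10.5.

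**5. How the late scan is classified.** SAP 6.2 generally uses scheduled visits as the analysis visit and maps only unscheduled, early-termination and end-of-study visits by actual day. A scan entered under the scheduled Day 1 visit would therefore keep that label, while SAP 5.1 denies it baseline status. A scan entered as unscheduled would be mapped by date, and for a parameter whose only Main Study visit is Week 24 that window opens at Study Day 2. Even then, a valid scheduled Week 24 scan is selected ahead of it. The SAP does not say which case applies.

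**6. Size, by assumption only.** The documents give no count. Let f be the fraction of subjects first scanned on Days 2 to 8. With an unchanged standard deviation, the standard error of mean change grows by 1/sqrt(1 - f):

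- f = 10%: 1/sqrt(0.9) = 1.054, or 5.4% larger.
- f = 20%: 1/sqrt(0.8) = 1.118, or 11.8% larger.

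In the 15 mg QW arm (16 planned, capped at about 20 in SAP 3.3), 10% is 1.6 to 2 subjects.

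**The case against.** The best counter-argument is intent. The protocol's summary of changes describes the widened window as one for post-treatment DXA, so the 7 late days may never have been meant for Day 1. That is plausible, but sites work from note r, and note r carries no such limit in either document. The MRI-PDFF note in the same table shows how the limit is written when wanted: "On treatment, MRI-PDFF should ideally be done within ± 7 days of the target visit date".

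Exposure may also be small. Version 4.0 of the protocol is dated 05 December 2022, and randomization was already running when the ratio changed in April 2022. Many first scans may therefore have been done under an earlier note whose window we cannot see. Under Amendment 1, an out-of-window DXA needed Medical Monitor approval. Nothing in the documents shows that any subject was scanned on Days 2 to 8. This stands, and it limits what can be said about size.

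The X code adds little. SAP 5.1 accepts any value from the first-dose day, before or after the injection. Refusing post-dose values as baseline is also a sound general rule; the looseness is in the schedule note.

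A reader might infer three stronger things, and the documents support none of them:

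- **That the late scan is analyzed as on-treatment data.** SAP 6.2 generally keeps scheduled visits at their nominal visit, so this is not established. What is established is that the classification is unclear.
- **That affected subjects leave the BMD analysis altogether.** They stay in the absolute-value summaries.
- **That a known share of the data or a planned comparison is lost.** The percentages above are illustrations, and the BMD analysis has no test or powered contrast.

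**Conclusion.** The conflict is real and narrow. Read as written, the two texts leave a dosed subject whose first DXA falls on Study Days 2 to 8, with no usable earlier scan, without change or percent change in BMD at Weeks 24 and 48, although the site followed the schedule. That is 7 of the 22 permitted dates; it is not an estimate of the share of subjects, which cannot be derived from the documents.

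The loss is of descriptive safety information. It does not touch the efficacy endpoints or any hypothesis test. The conclusion assumes that note r applies to the whole row, as its placement indicates, and that SAP 5.1 is applied to BMD without an unstated exception. If the sponsor confirms that every first scan was done no later than the first-dose day, there is no consequence for the data and only the wording needs repair.

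**What to change.** 1. **SAP 5.1.** Keep the present rule for BMD and add a fallback: if a dosed subject has no scan dated up to and including the first-dose day, the earliest scan through Study Day 8 serves as baseline, is flagged, and is never used as a post-baseline value. Scans before Study Day -14, which SAP 5.1 already accepts, remain acceptable.
2. **Note r (Protocol 1.3 and SAP Appendix 1).** State that the 7 late days apply to post-baseline scans only, and that the Day 1 DXA is to be done no later than the day of first dose.

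The two parts are complementary: the second prevents new cases, and the first covers those that already exist. If enrolment has closed, only the first has any effect. It would also help to report the number of flagged baselines by arm.

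The cost is one SAP sentence before database lock and a clarification of one note. SAP 5.1 already has measure-specific rules, so the sentence fits its structure. The downside is that a few flagged baselines follow dosing: one dose on the Q2W regimen, and one or two on QW, where the second dose is nominally on Study Day 8. Repeating the change summaries without the flagged subjects would show whether this matters.

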5.2. Actual Treatment Group

Primary Analysis for Main Study

If a subject receives only placebo doses, then their actual treatment group will be placebo group. If a placebo subject incorrectly received at least one pegozafermin active dose, then they will be counted as the pegozafermin active treatment group in the highest dose group received for safety analysis. If a pegozafermin subject receives at least one dose of pegozafermin active treatment, then the most frequent dose received will be considered as the actual treatment group.

Final Analysis

In the final analysis, the actual treatment arm will be assigned following the same rule as in the primary analysis for Main Study for subjects who were not re-randomized in the Extension study.

The actual treatment group will be assigned as pegozafermin in the highest dose level if subject switched from Placebo to pegozafermin in the Extension Study. However, subjects who switched the treatment in the Extension Study will be summarized under ‘Placebo (main) and

Pegozafermin 30 mg QW (Extension)" group as a separate column in the final safety summaries and efficacy analysis.

5.3. Study Day

The day a subject receives their first dose of IP will be considered as Study Day 1.

If a subject is randomized but never dosed, study day will be calculated using the randomization date and randomization date will be set to Study Day 1.

If date of interest occurring on or after the relative date, relative day is calculated as: date of interest – relative date + 1, else if date of interest occurring prior the relative date, relative day is calculated as: date of interest – relative date. Data will be presented on listings in order of site number/subject number, assessment date and assessment (in order collected on CRF, unless specified otherwise). Dates will be presented in the format of YYYY-MM-DD.

5.4. Prior Medication, Concomitant Medication / Procedures

Any medication that was stopped prior to the Study Day 1 is considered as prior medication.

Any medication/procedure that is taken any day on or after Study Day 1 is considered as concomitant medication/procedure. This includes medications/procedures that were started prior to administration of first dose and that were continued to be taken after Study Day 1.

5.5. Treatment Emergent Adverse Event (TEAE)

TEAE during the Main Study

All AEs started or worsened within the first dose of IP up to the min of (the last dose date before the completion of all Week 24 assessments in the Main Study IP+28 days, the date all Week 24 assessments completed, Main Study cut-off date) will be considered as TEAEs during the Main Study. For subjects who withdraw consent from the Main Study, the end date of the TEAE reporting period should be the earlier of the withdrawal consent date and the date of the last dose of the IP + 28 days.

TEAE during the Study

All AEs that started or worsened on or after the first dose of study IP up to the last dose of the study IP+28 days will be considered as TEAEs.

For subjects who withdraw consent from the study, the end date of the TEAE reporting period should be the earlier of the withdrawal consent date and the date of the last dose of the IP + 28 days.

6. ANALYSIS POPULATIONS

For purposes of analysis, the following populations are defined:

Population	Description
Randomized Analysis Set	All enrolled subjects who are assigned a randomization number in the study.
Full Analysis Set (FAS)	All enrolled subjects with confirmed fibrosis stage F2 or F3 and NAS ≥ 4 at baseline per independent review by a 3-pathologist panel who are eligible and assigned a randomization number in the study and received at least 1 dose of IP. For analysis purposes, subjects will be analyzed according to the treatment they were randomized to regardless of actual treatment received.
Safety Analysis Set	All randomized subjects who receive at least 1 dose of IP. In this population, subjects will be summarized based upon the IP actually received, regardless of the IP to which they were randomized.
PK Analysis Set	All subjects in the FAS who have sufficient data to adequately characterize the trough serum pegozafermin concentrations and have no other events or protocol violations that would adversely affect results, such as not completing the full dose. The analysis population for any population PK modeling may be defined separately in a population PK data analysis plan.
MRI-PDFF Analysis Set	All subjects in the Full Analysis Set who have a baseline and at least one follow up MRI-PDFF assessment.

Primary Analysis

- Patient dispositions and screen failure summary will be presented for all subjects screened.
- Baseline characteristics, protocol deviations, medical histories and concomitant medications will be assessed for Randomized Analysis Set.
- All primary, secondary, and exploratory efficacy endpoints of Main Study will be assessed for Full Analysis Set.
- Exposure and safety assessments will be analyzed based on Safety Analysis Set.
- PK endpoints will be displayed and analyzed for all subjects with applicable data in the PK Analysis Set.

Final Analysis

- Protocol deviations and concomitant medications will be summarized based on Randomized Analysis Set including data in Extension Study.
- Exposure and safety assessments will be summarized based on Safety Analysis Set including data in Extension Study.
- PK endpoints will be displayed and analyzed for all subjects with applicable data in the PK Analysis Set.

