- Repeating liver enzymes, serum bilirubin, hematology panel (for eosinophil count), and INR tests two or three times weekly. Frequency of repeat testing can decrease to once a week or less if abnormalities stabilize or the IP has been discontinued and the subject is asymptomatic.
- Obtaining a more detailed history of symptoms and prior or concurrent diseases.
- Obtaining a history of concomitant drug use (including nonprescription medications and herbal and dietary supplement preparations), alcohol use, recreational drug use, and special diets.
- Ruling out acute viral hepatitis types A, B, C, D, and E; autoimmune or alcoholic hepatitis; hypoxic/ischemic hepatopathy; and biliary tract disease.
- Obtaining a history of exposure to environmental chemical agents.
- Obtaining additional tests to evaluate liver function, as appropriate (e.g., INR, direct bilirubin).
- Considering gastroenterology or hepatology consultations.

Note: If a visit to the clinic is not feasible, laboratory testing can be performed by home health and sent to the central laboratory, or locally and the results should be promptly communicated to the Investigator site.

7.1.2. Monitoring and Study Continuation of Subjects with NASH Fibrosis Stage F1 or F4

The initial protocol allowed subjects to be included based on the biopsy read by one of the 2 expert pathologists. Version 3 Amendment #2 (March 11, 2022) changed the biopsy reading methodology to a central panel of 3 independent pathologists. This change in methodology

resulted in a change in fibrosis stage at baseline for some subjects (from F2 or F3 to either F1 or F4). These subjects and subjects evaluated as F4 during the study will be managed as follows:

1. Subjects with baseline fibrosis stage F1 as determined by a consensus of 3 central pathologists may continue all phases of the study and will be analyzed separately as an exploratory population.
2. Subjects with baseline fibrosis stage F4 (cirrhotic) as determined by a consensus panel of 3 central pathologists (as described above) will participate in all phases of the study as an exploratory population and will be analyzed separately provided:
 - a. Their liver disease is considered well compensated as assessed by Child-Pugh Class A criteria (See Section 10.8), and
 - b. There is no evidence of hepatic decompensation (i.e., hepatic encephalopathy, ascites, or bleeding varices) as assessed by the PI according to usual standard of care, and

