7.11. Serum concentration of pegozafermin

The serum concentration of pegozafermin over time will be listed by individual and summarized for each timepoint by treatment group. Serum concentration data will also be presented using arithmetic statistics. Individual and mean pegozafermin serum concentration vs. time plots will be produced on both a linear scale and on a semi-logarithmic scale.

For summarization of PK concentration values and data analysis, assessments that are below the lower limit of quantification (LLOQ) will be set to zero prior to summarization. For PK concentration graphs using a semi-logarithmic scale, assessments that are below the lower limit

of quantification will be set to half of LLOQ prior to graphing for illustration purposes. For PK concentration assessments that are above the upper limit of quantification (ULOQ), the record will be set to missing prior to summarization or graphing.

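### The PK Analysis Set is nested in the histology-defined FAS, so treated subjects with panel-read baseline F1, F4 or NAS below 4 are left out of the planned trough displays

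*SAP*

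**What the plan says.** SAP section 6 and Protocol 9.3 define the populations in the same words. The PK Analysis Set is "All subjects in the FAS who have sufficient data to adequately characterize the trough serum pegozafermin concentrations", with no events or violations that would harm the results. The FAS from which it is drawn is "All enrolled subjects with confirmed fibrosis stage F2 or F3 and NAS ≥ 4 at baseline per independent review by a 3-pathologist panel", further limited to eligible, randomised and dosed subjects, and analysed by randomised arm. The Safety Analysis Set has no histology condition: "All randomized subjects who receive at least 1 dose of IP", summarised by the product actually received.

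SAP section 6 then states, for both the primary and the final analysis: "PK endpoints will be displayed and analyzed for all subjects with applicable data in the PK Analysis Set". SAP 7.11 gives the content: "The serum concentration of pegozafermin over time will be listed by individual and summarized for each timepoint by treatment group". It has no breakdown by fibrosis stage.

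Protocol 7.1.2 explains that moving to a three-pathologist panel changed some subjects' baseline stage to F1 or F4. F1 subjects may continue in all phases and be analysed separately. F4 subjects who meet the listed conditions "will participate in all phases of the study as an exploratory population and will be analyzed separately".

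**The concern.** A histology condition serves an efficacy population that must match the target disease stage. It has no stated purpose when the aim is to describe serum drug levels in people who were given the drug. Here it comes in only because the PK set is built on the FAS.

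Two things are at stake. First, trough concentration is a secondary endpoint, and usable values from treated subjects would have no planned display. This includes the baseline F4 subjects, whom the protocol treats as a group to be reported in its own right. Second, the impact of anti-drug antibodies on concentrations is a listed safety endpoint (SAP 4.1.5 and 4.2.3). The antibody results and the concentrations that would be set against them come from different populations.

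**Working it through.** No figure in the plan depends on this point, so the check is one of set membership and cross-reading.

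**Step 1. Who is in which set.** Take a dosed, pegozafermin-treated subject and apply the definitions in SAP section 6.

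| Panel read | Safety Analysis Set | FAS | PK Analysis Set |
|---|---|---|---|
| Baseline F2 or F3, NAS 4 or more | yes | yes | yes, if trough data suffice |
| Baseline F1 | yes | no | no |
| Baseline F4 | yes | no | no |
| Baseline NAS below 4 | yes | no | no |
| Baseline F2 or F3, NAS 4 or more; F4 first read at Week 24 | yes | yes | yes, if trough data suffice |

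Three groups of treated subjects are in the Safety Analysis Set and outside the PK Analysis Set.

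**Step 2. Are there such subjects?** Protocol 7.1.2 says that some subjects were restaged to F1 or F4 at baseline, and it lets them continue. SAP 7.8.1.2.3 plans a sensitivity analysis that adds back randomised and dosed subjects with F1, F4 or NAS below 4. Neither gives a count or an arm. By plan, 16 + 64 + 40 = 120 of the 184 subjects start on pegozafermin (SAP 3.5).

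**Step 3. Are their concentrations available?** Protocol 8.4 leaves unassayed only samples drawn while a subject is on placebo. No rule withholds assay by fibrosis stage.

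**Step 4. Is there another planned display for them?** SAP 7.11 summarises by timepoint and treatment group, and SAP 7.12.3 repeats the PK analysis with Extension data. Neither names F1 or F4. SAP 7.8.1.2.3 repeats the primary histology analysis only, and it pools these subjects instead of separating them. The separate analysis announced in Protocol 7.1.2 has no counterpart in the SAP for concentrations.

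**Step 5. Antibodies against concentrations.** SAP 7.10 puts safety analyses, including immunogenicity (7.10.6), on the Safety Analysis Set. Concentrations are on the PK Analysis Set. A cross-tabulation or plot of one against the other would have antibody results but no in-set concentration for the three excluded groups.

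**Step 6. Grouping.** The FAS follows the randomised arm, the Safety Analysis Set follows the product received, and SAP 7.11 says only treatment group. The PK displays are therefore not tied explicitly to the drug actually given.

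**The case against.** The best defence is that trough levels are wanted in the subjects whose histological response is being interpreted. Protocol 4.2 ties Phase 3 dose selection to this study's efficacy data, in particular histology, and those analyses use the FAS. Describing concentrations in the same population is coherent, and the two documents agree with each other. This stands as a reason to keep the panel-confirmed display. It is not a reason to have no other.

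Several stronger readings are tempting, and the documents do not support them.

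- *That the data are lost or discarded.* Samples taken on active drug are assayed whatever the stage. The PK definition also adds "The analysis population for any population PK modeling may be defined separately in a population PK data analysis plan", so a model could use these values. That route is optional and commits to no trough summary.
- *That exposure in cirrhosis is never summarised.* Extent of dosing is covered: "Exposure and safety assessments will be analyzed based on Safety Analysis Set", and that set includes baseline F4 subjects, though pooled. Subjects first read as F4 at Week 24 stay eligible for the PK set. The gap concerns serum concentration in baseline F4 subjects.
- *That monitoring of F4 subjects suffers.* Protocol 7.1.2 bases it on Child-Pugh class, signs of decompensation, assessment for hepatocellular carcinoma and MELD Na. No concentration enters. Protocol 6.4.3 keeps PK results after Day 1 blinded unless otherwise specified.
- *That the trough summaries lose a known amount of precision.* The share of treated subjects who fail the panel read is nowhere given, and the summaries are descriptive, so no test would be affected.

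It is also fair that the antibody evaluation is optional (Protocol 9.4.2 says only that it may be done) and that SAP 7.10.6 specifies no such table. The mismatch would affect that evaluation if it is run; it breaks no analysis now specified.

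**Conclusion.** The point holds in a limited form. Treated subjects with panel-read baseline F1, F4 or NAS below 4 are excluded from the planned trough displays by a criterion that has no stated bearing on drug levels. No concentration summary is specified for baseline F4 subjects, despite the separate analysis announced in Protocol 7.1.2.

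The size in subjects cannot be stated from the documents. What follows from the definitions alone is that the exclusion is total for each of the three groups. The practical consequence assumes that at least one such subject received pegozafermin. That is likely when 120 of 184 are planned to start on it, but neither document says so. The effect is confined to descriptive PK output and to any optional evaluation of antibodies against concentrations.

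**What to change.** In SAP section 6, define the PK Analysis Set as Safety Analysis Set subjects who received pegozafermin and have at least one evaluable post-dose trough, grouped by actual treatment under SAP 5.2. Say what makes a trough evaluable. In the final analysis, keep subjects who switched from placebo to 30 mg QW in the column SAP 7.12 already gives them.

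In SAP 7.11, retain the panel-confirmed F2/F3, NAS 4 or more subset as a display. List or summarise baseline F1 and baseline F4 subjects separately; a listing is enough if they are few. State that any evaluation of antibodies against concentrations uses the revised set.

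The cost is a change of wording and one more descriptive display from data already collected. Protocol section 9 gives the SAP precedence on analyses, so Protocol 9.3 can be aligned at the next amendment. Sample size, power, alpha and all efficacy results are unchanged.
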